4 TRIAL DESIGN AND METHODS

4.1 Overview

This study is a prospective, double-blind, multi-center, placebo-controlled safety and efficacy study of methylprednisolone in infants undergoing planned heart surgery with CPB. The study will enroll up to 1500 infants (< 1 year of age) including a minimum of 400 neonates \leq 30 days at the time of surgery. The total study duration is expected to be approximately 48 months. An ancillary PK/PD/Biomarker study will enroll subjects at select centers. This study is unique in that it is designed to leverage existing registry infrastructure at participating sites so as to reduce trial costs. Participants will be randomized and will receive a subject ID. This ID will also serve as a unique patient identifier allowing us to crosslink datasets. Participants will then receive study drug/placebo administered into the pump prime during cardiopulmonary bypass. All study participants will then receive routine post-operative care. Participating centers will enter all demographic, preoperative, operative and outcomes data into their existing institutional databases for submission to the STS-CHSD as they currently do. These data will be used to evaluate trial outcomes.

4.2 Procedures to Minimize/Avoid Bias

4.2.1 Randomization

Eligible participants will be randomized prior to their electively scheduled surgery in a 1:1 fashion to the treatment groups summarized in table 2 below. A block randomization scheme will be employed to ensure equal allocation by study site. Randomization assignments will be generated by a web-based system at the data coordinating center (DCC), after confirmation of trial eligibility. Trial sites will enter the randomization number into two databases that will be used for this trial (see section 6.4): the participating center's surgical database (for submission to the STS-CHSD), and an IBM Clinical Development database that will be used to capture some adverse event data, timing of drug delivery and timing of PK samples (for participating centers only) and a subset of laboratory values from the electronic health record.

Table T.	Study Drug	guusing
Group	Ν	Intra-operative
1	up to 750	IV methylprednisolone in the CPB prime
2	Up to 750	Placebo

Table 1. Study Drug dosing

4.2.2 Blinding

The study medication and the placebo will be identical in appearance to assure masking of study medication. The randomization assignment will be seen only by the statistician at the DCC and the investigational pharmacist preparing the study medication. The family/subject, study coordinator and investigators will remain masked as to treatment group assignment until after all trial data are analyzed.

4.3 Study measures

Study outcomes were determined after trial simulations. Based upon these data we selected the following primary and secondary outcome measures.

4.3.1 **Primary Endpoint**

A composite mortality, major morbidity and length of stay global rank endpoint with endpoints ranked according to severity. The global rank score has been previously described.[23] Subjects will receive a rank score based upon the lowest ranking (worst) endpoint that they experience during the study trial.

Rank Score	Description
1	Operative mortality
2	Heart transplant (during hospitalization)
3	Renal failure with permanent dialysis, neurologic deficit persistent at discharge, or respiratory failure requiring tracheostomy
4	Post-operative mechanical circulatory support or unplanned cardiac reoperation (exclusive of reoperation for bleeding)
5	Reoperation for bleeding, delayed sternal closure, or post-op unplanned interventional cardiac catheterization
6	Post-op cardiac arrest, multi-system organ failure, renal failure with temporary dialysis, or prolonged ventilator support (> 7 days)
7	Post-operative length of stay > 90 days
8-97	Post-operative length of stay

Table 2. Global Rank Endpoint Details

4.3.2 Secondary Endpoints (see section 11.2 for data element definitions)

Efficacy:

- Mortality including in-hospital mortality or mortality after hospital discharge but within 30 days of the last dose of study drug
- Death or major complication as defined by an outcome in one of the 6 highest global ranking categories
- Post-operative hospital length of stay
- Prevalence of prolonged (> 7 days) post-operative mechanical ventilation

• Occurrence of post-operative low cardiac output syndrome

Safety:

- Occurence of any one or more of the following STS-CHSD-defined major post-operative infectious complications:
 - Postprocedural infective endocarditis
 - o Pneumonia
 - o Sepsis
 - Deep wound infection
 - Mediastinitis
- Other post-operative complications will be collected from the start of study drug/placebo administration until hospital discharge.

PK/PD/Biomarkers:

- Time to maximum concentration (T_{max})
- Maximum concentration (C_{max})
- Clearance (CL)
- Volume of distribution (Vd)
- Post-operative blood markers of inflammation

PK/PD and Biomarker data will only be collected at select centers and in those patients whose parent/legally authorized representative have granted consent to blood draws. An opt in/out clause is included in the informed consent forms for study participants and centers will be allowed to participate in this part of the study if they prefer. Parent/legally authorized representative of participants may elect to participate in the PK/PD, the Biomarker studies or both. Time points for blood collection will be the same for both the PK/PD and biomarker studies. Biomarkers being collected represent blood markers of inflammation.

4.3.3 Timeframe for collection of safety and efficacy endpoints

With respect to primary and secondary outcome measures, participants will be followed for the duration of their hospitalization. Data will be collected consistent with standard STS-CHSD reporting protocol. Participants that are discharged within the first 30 days after their initial cardiac surgery, or any participants that receive study drug/placebo but then do not undergo surgery, will be followed to assess for mortality through 30 days after administration of study drug/placebo. If patients remain hospitalized for > 4 months after the final study subject has been enrolled then they will be assigned the worst rank outcome that they have encountered to that point. Patients still hospitalized with mechanical circulatory support and listed for heart transplant will assigned to the "heart transplant" outcome (See missing data section for exceptions). Serious study drug-related adverse events will be collected through 7 days after administration of study drug. Based upon an 18 hour estimated half- life of methylprednisolone, this duration of follow up (> 10 half-lives) will ensure collection of all potentially study drug-related serious adverse events but avoids capturing unnecessary serious adverse events in this high morbidity patient population.

4.4 Schedule of events

Participants will be enrolled at the time of their electively scheduled surgery. Sites will receive a randomization ID that will be entered into the two relevant databases: the sites' surgical database (STS-

Page 10 of 96

CHSD), and an IBM Clinical Development clinical database. The study drug/placebo will be administered in the CPB pump prime at the time of initiation of CPB. Participants will then undergo surgery with CPB per standard of care. Participants will receive routine post-operative care. Post-operative outcomes including post-operative hospital length of stay, discharge mortality, and complication data will be recorded in the sites institutional surgical database (STS-CHSD) consistent with current practices at the enrolling sites. STS-CHSD data element definitions of particular relevance to the STRESS trial are included in Section 11.2. A subset of additional safety endpoints and select safety laboratory values from the electronic health record will be collected into a separate clinical database, IBM Clinical Development (see section 6.4). Plasma samples including PK/PD/Biomarker samples will be evaluated in a subset of enrolled patients at select centers using a limited sampling scheme. Sample acquisition, handling, and shipping instructions are outlined in Appendix C.

|--|

Procedure	Pre-	Day 1	Day 2	Day 3	Day 4-7	Duration of
	dose					hospitalization ³
Informed Consent	Х					
Demographics	Х					
Physical Exam	Х					
Medical History	Х					
Elective surgery with CPB		Х				
Administer study drug/placebo ¹		Х				
Timed PK/PD/Biomarker Samples ²		Х	Х			
Study drug-related SAEs	Х	Х	Х	Х	Х	
STS-CHSD data (1° / 2ndary endpoints)		Х	Х	Х	Х	Х

¹Study drug/placebo will be administered at the time of initiation of CPB

² Specific times of PK/PD/Biomarker sampling TBD based upon preliminary analysis of an on-going population PK study

³ Mortality data will be collected for the duration of hospitalization or until 30 days after study drug / placebo administration for patients that are discharged. If patients remain hospitalized for > 4 months after the final study subject has been enrolled then mortality data for the hospitalization will not be collected and they will be assigned the worst rank outcome that they have encountered to that point.

5 SELECTION AND WITHDRAWAL OF SUBJECTS

5.1 Inclusion criteria

- 1. Age < 1 year at the time of surgery
- 2. Planned heart surgery with CPB as part of standard clinical care.
- 3. Availability and willingness of the parent/legally authorized representative to provide written informed consent.

5.2 Exclusion criteria

- 1. < 37 weeks adjusted gestational age at time of surgery
- 2. Any oral or intravenous steroid treatment within two days of surgery
- 3. Any patient receiving any of the following medications within 2 days of surgery:

Amphoteracin B, aminoglutethimide, anticholesterases, warfarin, P450 3A4 inducers

Page 11 of 96

including (but not limited to) carbamazepine, phenobarbital, phenytoin, rifampin, bosentanand nafcillin or P450 3A4 inhibitors including (but not limited to) clarithromycin, voriconazole, itraconazole, ketoconazole, ciprofloxacin, diltiazem, fluconazole, erythromycin, azithromycin and verapamil.

- 4. Infection contraindicating steroid use
- 5. Preoperative mechanical circulatory support or active resuscitation at the time of randomization
- 6. Previous enrollment in the STRESS trial

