	 Any oral or intravenous steroid treatment within two days of surgery Infection contraindicating steroid use Any patient receiving any of the following medications within 2 days of surgery: Amphoteracin B, aminoglutethimide, anticholesterases, warfarin, P450 3A4 inducers including (but not limited to) carbamazepine, phenobarbital, phenytoin, rifampin, bosentan and nafcillin or P450 3A4 inhibitors including (but not limited to) clarithromycin, voriconazole, itraconazole, ketoconazole, ciprofloxacin, diltiazem, fluconazole, erythromycin, azithromycin and verapamil. Preoperative mechanical circulatory support or active resuscitation at the time of randomization Previous enrollment in the STRESS trial
Estimated Start:	September 2017
Estimated Finish:	August 2021
Primary endpoints	 Primary efficacy and safety outcome measures will be compared between infants receiving any methylprednisolone and placebo. Primary endpoint - efficacy: The primary outcome measure will consist of a composite mortality, major morbidity and length of stay global rank endpoint with endpoints ranked according to severity. For this endpoint each randomized patient recieving study drug will be assigned a rank based upon their most-severe outcome.
Secondary endpoints	 Efficacy: Mortality including in-hospital mortality or mortality after hospital discharge but within 30 days of the last dose of study drug Death or major complication as defined by an outcome in one of the 6 highest global ranking categories Post-operative hospital length of stay Prevalence of prolonged (> 7 days) post-operative mechanical ventilation Occurrence of post-operative low cardiac output syndrome Safety: Occurence of any one or more of the following major post-operative infectious complications: Postprocedural infective endocarditis Pneumonia Sepsis Deep wound infection Mediastinitis Other post-operative complications will be collected from the start of study drug administration until hospital discharge. PK/PD/Biomarkers: Time to maximum concentration (T_{max}) Maximum concentration (C_{max}) Clearance (CL) Volume of distribution (Vd) Post-operative blood markers of inflammation

	Blood samples will be obtained from patients at various time points after the study drug infusion. PK parameters will be estimated by non-compartmental analysis using
DK/DD/Biomarkors	WinNonLin software. Study participants as well as enrolling centers will be given the

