6 STUDY PROCEDURES

6.1 Preoperative Assessment – Screening Procedures and Baseline

Measurements

- 1. Obtain a signed and dated Informed Consent Form (ICF) prior to any study related procedures.
- 2. Enter all demographic, preoperative risk factor and past medical/surgical history data into the STS-CHSD as per routine
- 3. Obtain a unique subject ID from the IBM Clinical Development database. This subject ID will also serve as a unique patient identifier allowing cross-linking across databases. It must also be entered into the site's surgical database under the study identifier tab as the "STS-related clinical trial ID" (see section 6.4). In addition the STS "Operation ID" must be entered into both databases and will serve as a double check in the event that the IBM Clinical Development subject ID is incorrectly entered into either of the 2 databases.
- 4. Perform routine preoperative assessment

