6.2 Baseline/Pre-Dose Assessment

After the parent or legally authorized representative has signed the IRB-approved informed consent form, and after it has been determined that the patient satisfies all inclusion and exclusion criteria, the following evaluations will be performed and entered directly into the study database (STS-CHSD):

1. Baseline demographics (race, gender, date of birth, age, weight, age and weight at surgery)

Version 6.0

- 2. Fundamental cardiac diagnosis as defined by the STS-CHSD
- 3. Presence of any of the 41 STS-CHSD defined preoperative risk factors including mechanical ventilation to treat cardiorespiratory failure, sepsis, stroke, renal failure or hepatic dysfunction as defined by the STS-CHSD.
- 4. Presence of any non-cardiac anatomic abnormality, genetic syndrome or chromosomal anomaly as defined by the STS-CHSD.

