7 TREATMENTS TO BE ADMINISTERED

7.1 Description of Study Treatments

Eligible subjects will be randomized prior to their electively scheduled surgery in a 1:1 fashion to methylprednisolone (30mg/kg) versus placebo as summarized in table 2 above. The dosages for administration (30 mg/kg) are based upon expert consensus regarding current practice and a previous dosing study. Intravenous methylprednisolone is available in a **preservative free** single use "Act-O-Vial Page 14 of 96

System" containing powder (40mg, 125mg, 500mg and 1000mg options are available) and diluent. Study drug will be provided "off the shelf" by study sites and prepared following local pharmacy protocols. Only preservative-free solutions will be used for this trial due to safety concerns with the administration of benzyl alcohol preservatives in infants. Study drug will be mixed with isotonic saline in a syringe to create a solution. Placebo preparations will consist of isotonic saline only and will be prepared in identical syringes so as to be physically indistinguishable from study drug.

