Rheumatic disorders: As adjunctive therapy for short-term administration (to tide the patient over an acute episode or exacerbation) in acute gouty arthritis; acute rheumatic carditis; ankylosing spondylitis; psoriatic arthritis; rheumatoid arthritis, including juvenile rheumatoid arthritis (selected cases may require low-dose maintenance therapy). For the treatment of dermatomyositis, temporal arteritis, polymyositis, and systemic lupus erythematosus.

CONTRAINDICATIONS

SOLU-MEDROL Sterile Powder is contraindicated:

- in systemic fungal infections and patients with known hypersensitivity to the product and its constituents.
- for intrathecal administration. Reports of severe medical events have been associated with this route of administration.

Intramuscular corticosteroid preparations are contraindicated for idiopathic thrombocytopenic purpura.

Additional contraindication for the use of SOLU-MEDROL Sterile Powder preserved with benzyl alcohol:

Formulations preserved with benzyl alcohol are contraindicated for use in premature infants. (See WARNINGS and PRECAUTIONS, Pediatric Use.

WARNINGS

Serious Neurologic Adverse Reactions with Epidural Administration

Serious neurologic events, some resulting in death, have been reported with epidural injection of corticosteroids. Specific events reported include, but are not limited to, spinal cord infarction, paraplegia, quadriplegia, cortical blindness, and stroke. These serious neurologic events have been reported with and without use of fluoroscopy. The safety and effectiveness of epidural administration of corticosteroids have not been established, and corticosteroids are not approved for this use.

GENERAL

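### Known hypersensitivity to methylprednisolone or its constituents, a contraindication in the appended label, is missing from the exclusion criteria in section 5.2 and the synopsis

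*Combined protocol and SAP*

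**What the plan says.** Section 5.1 has three inclusion criteria: age, planned bypass surgery and parental consent.

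Section 5.2 has six exclusions:

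1. adjusted gestational age below 37 weeks;
2. oral or intravenous steroids within two days of surgery;
3. a list of interacting drugs within two days;
4. "Infection contraindicating steroid use";
5. preoperative mechanical support or active resuscitation;
6. earlier enrolment in the trial.

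The synopsis lists the same six in a different order. Its last two are "Preoperative mechanical circulatory support or active resuscitation at the time of randomization" and earlier enrolment, and nothing follows them.

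These lists decide who enters. Section 6.2 starts the baseline evaluations "after it has been determined that the patient satisfies all inclusion and exclusion criteria", and section 4.2.1 generates the assignment "after confirmation of trial eligibility".

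The package insert in Appendix B (section 15.3), under Contraindications, rules the product out "in systemic fungal infections and patients with known hypersensitivity to the product and its constituents". Its adverse-reaction section lists anaphylaxis and angioedema, and its warnings describe anaphylactoid reactions as rare.

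**The concern.** One sentence of the label names two patient-level contraindications, and the protocol carries over only the first. The protocol clearly drew on the label elsewhere. Exclusion 3 follows the label's drug-interaction section closely and turns into exclusions several items that the label mostly handles by monitoring or dose adjustment. An outright contraindication was left out, and no reason is given, so this reads as an oversight.

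The eligibility list is the right place for it. Once an infant is randomized, chance decides whether the drug is given, and section 7.3 blinds the people giving it. The exposure is 30 mg/kg as a bolus into the pump prime (sections 7.1 and 7.2). The possible harm to an individual infant is serious even though the chance is small.

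**Working it through.** No calculation applies. The check sets the label's contraindications against the eligibility criteria and then looks for anything else in the protocol that would close the gap.

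**Label contraindications (Appendix B) against this trial**

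| Label contraindication | Relevant here? | Covered? |
|---|---|---|
| Systemic fungal infection | Yes | Yes, exclusion 4 |
| Known hypersensitivity to product or constituents | Yes | No |
| Intrathecal administration | No, drug goes into the bypass prime (7.2) | – |
| Intramuscular use in idiopathic thrombocytopenic purpura | No, same reason | – |
| Benzyl-alcohol formulations in premature infants | No, preservative-free drug only (7.1) | – |

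Of 5 contraindications, 3 do not apply to this route and formulation, which leaves 5 − 3 = 2. One of those 2 is covered. The benzyl-alcohol item could instead be counted as relevant and covered, by the preservative-free requirement and the 37-week exclusion. Coverage is then 2 of 3. On either count the one left uncovered is hypersensitivity.

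**Eligibility criteria**

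- Exclusions (5.2): 6, none naming hypersensitivity.
- Inclusions (5.1): 3, none naming it.
- Total: 6 + 3 = 9, of which 0 address it.
- Items excluding any other contraindication, or leaving exclusion to the investigator: 0, in sections 5.1 to 5.4, 6.1, 6.2 or the synopsis.

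Both exclusion lists appear complete and match item for item, so the gap is not a result of text lost from the PDF.

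**Does the protocol make the label part of eligibility?** No. Its body refers to the label for expectedness of adverse events (9.4), the site study file (12.4), pharmacology and toxicology (13) and previous human experience (14).

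**Could an infant have known hypersensitivity?** Yes, though rarely. Eligibility runs to one year of age, and steroids are barred only in the two days before surgery, so earlier exposure is allowed. Section 3.1 cites a registry of more than 25,000 infants having bypass operations in which 57% received perioperative corticosteroids, so an infant returning for a second operation may already have been exposed. The label also covers constituents: the 40 mg preservative-free vial, one of the options in section 7.1, contains lactose.

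**The case against.** The strongest reply is that no consequence has been shown. A known reaction must already have been documented in an infant under one year, and at least 400 participants are to be 30 days old or younger. The documents give no rate, and the affected group could be empty.

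Several steps would also probably catch such a case. The schedule of events includes "Medical History" before dosing, and section 6.1 tells sites to "Perform routine preoperative assessment". Study drug is "prepared following local pharmacy protocols", and the investigational pharmacist knows the assignment (4.2.2). Section 12.6 requires the risks to be discussed with the parent. The drug is given in an operating room, emergency unblinding is available (8.2), and drug-related serious events must be reported within one business day (9.1).

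The fix is not entirely free either. Section 12.1 requires ethics approval of amendments at each site, with up to 40 sites planned. Version 6.0 is dated 27 March 2022, and the rationale for Amendment 5 mentions patients still hospitalized at the end of the study, so few or no later infants might benefit.

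Most of this stands, and it is why the point is minor. It does not remove the gap. None of these steps is a stated exclusion, and none tells anyone to ask about steroid or excipient allergy before randomization. Unblinding and event reporting come into play only after exposure. Site approval is a routine cost that can be carried by any amendment. Late timing reduces the urgency but does not make the criteria correct.

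**Conclusion.** The concern holds, as a minor patient-safety omission. Of the two label contraindications that apply to this route and formulation, section 5.2 and the synopsis cover one, and 0 of 9 eligibility criteria address known hypersensitivity. An infant who is otherwise eligible and has this contraindication passes the rule as written.

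No number of affected infants is claimed. That the condition is rare under one year of age is an assumption, because the documents give no rate. The conclusion rests on the protocol and its appendices; any site-level eligibility checklist outside them was not available. It has no bearing on the primary endpoint, the type I error, the power or the analysis.

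**What to change.** Add to section 5.2 and to the synopsis an exclusion for known hypersensitivity to methylprednisolone or any constituent of the study drug formulation. Include it in the eligibility confirmation that section 4.2.1 already requires before randomization.

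The text change is one line in each place plus one check at an existing step. It needs ethics approval at each site under section 12.1 and can go with any other amendment. The loss of recruitment is expected to be negligible, and there is no statistical consequence.
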